1.3 RATIONALE FOR DOSE SELECTION

A single dose of 600 mg (3 × 200 mg capsules) TPOXX was chosen as this is the recommended dose for TPOXX.

Sevelamer carbonate, sucroferric oxyhydroxide, calcium acetate, and lanthanum carbonate were chosen for this study because they are common phospate binders that patients prescribed TPOXX may be concurrently taking. The planned doses for each of these drugs were selected based on the FDA Guidance "Clinical Drug Interaction Studies - Study Design, Data Analysis, and Clinical Implications", which states the maximum dose and the shortest dosing interval should be used.²

Any potential DDI will be determined based on an analysis of TPOXX PK in the presence of phosphate-binding drugs. The planned doses of TPOXX and the 4 phosphate binders are expected to be sufficiently high to quantify an effect on TPOXX plasma exposure levels.

1.4 POTENTIAL RISKS AND BENEFITS

1.4.1 Potential Risks

The effect of TPOXX on a fetus or nursing baby is not yet known; therefore, women of childbearing potential participating in this study will be required to agree to use an acceptable means of birth control from signing of the informed consent form (ICF) and continuing through 30 days after the last dose of study drug. Pregnancy testing will be performed at the screening visit and checked by the investigator for negative pregnancy on Day –1 of each period before administration of study drug. Women who are pregnant or lactating or plan to become pregnant within 3 months after study drug administration will be excluded from the study; if a female subject becomes pregnant during study participation, study drug dosing will be discontinued, and the subject will be withdrawn from the study (Section 6.2.1.8).

As with all drugs, there is potential risk of an allergic reaction. At this time, there is no definitive information on the allergic activity of TPOXX. Headache and nausea have been the most common adverse events (AEs) in clinical studies completed to date. There may be other side effects of TPOXX that are not yet known. Full details can be found in the TPOXX full prescribing information.³

A single dose of the phosphate binders should not lead to any major AEs, but there may be an increased risk of hypercalcemia (specifically with calcium acetate). Other potential AEs include diarrhea, dyspepsia, nausea, vomiting, abdominal pain, flatulence, and hypotension (specifically with sucroferric oxyhydroxide).

1.4.2 Known Potential Benefits

As this study will be conducted in subjects free from smallpox, no direct health benefits from taking the study drug are expected. Study subjects may benefit from knowledge gained in this study which may aid in the use of TPOXX for the treatment of smallpox in patients taking phosphate binders.

Protocol: SIGA-246-023 (Version 2.0)

2. STUDY OBJECTIVES

2.1 PRIMARY OBJECTIVE

The primary objective of this study is to evaluate potential DDI as measured by the effect of coadministration of 4 separate phosphate binders on the PK of orally administered TPOXX in healthy adult subjects.

2.2 SECONDARY OBJECTIVE

The secondary objective of this study is to evaluate the safety and tolerability of 600 mg oral TPOXX administered with 4 different phosphate binders in healthy adult subjects.

3. STUDY DESIGN AND METHODOLOGY

This is a postmarketing, open-label, 5-period crossover drug interaction study designed to evaluate the potential effects of coadministration of 4 different phosphate binders on the PK of orally administered TPOXX in healthy adult subjects. A total of 44 subjects, ages 18 to 50, inclusive, will be enrolled and be randomly assigned to 1 of 4 treatment sequences. The study will consist of a screening period (Day –28 to Day –2), 5 treatment periods (Day –1 to Day 31), an end-of-study visit (Day 36 [+2 days]), and a follow-up telephone call (Day 59 [+4 days]). The treatment sequences and periods will be as follows:

Treatment Sequence	Period 1 Treatment	Period 2 Treatment	Period 3 Treatment	Period 4 Treatment	Period 5 Treatment
ABCDE	A	В	С	D	Е
ACEBD	A	С	Е	В	D
ADBEC	A	D	В	Е	С
AEDCB	A	Е	D	С	В

- Treatment A: A single oral dose of 600 mg (3×200 mg capsules) TPOXX.
- Treatment B: A single oral dose of 600 mg (3 × 200 mg capsules) TPOXX coadministered with a single oral dose of 1600 mg (2 × 800 mg tablets) sevelamer carbonate (Renvela® or generic equivalent).
- Treatment C: A single oral dose of 600 mg (3 × 200 mg capsules) TPOXX coadministered with a single oral dose of 500 mg sucroferric oxyhydroxide (Velphoro®) chewable tablet.

- Treatment D: A single oral dose of 600 mg (3 × 200 mg capsules) TPOXX coadministered with a single oral dose of 1334 mg (2 × 667 mg capsules) calcium acetate (PhosLo® generic equivalent).
- Treatment E: A single oral dose of 600 mg (3 × 200 mg capsules) TPOXX coadministered with a single oral dose of 500 mg lanthanum carbonate (Fosrenol® or generic equivalent) chewable tablet.

There will be a washout period of 7 days between dosing in each treatment period. All subjects will be provided a meal (consisting of approximately 600 calories and 25 g fat). The meal should be completed within 30 minutes. Subjects should be administered study drug as soon as possible following completion of the meal but no more than 30 minutes should elapse between meal completion and study drug administration. Study drug and meals must be taken with water only, and no other beverage except water should be ingested within 3 hours before or 3 hours after study drug administration. Water is allowed at all times throughout the study. Subjects must fast for 2 hours after taking study drug as further food consumption may affect drug absorption.

In each period, subjects will report to the study site on Day –1 and remain confined to the study site until 48 hours after dosing in Period 5 (Day 31). Subjects will be monitored for safety and tolerability. Serial blood samples for PK analysis of TPOXX will be collected before dosing (0 hour) and up to 48 hours after administration of the study drug(s).

All subjects will have a follow-up telephone call 30 days after administration of the last dose of study drug (Day 59 [+4 days]) to report any serious AEs (SAEs). At the time of discharge from the clinical research unit, subjects will be instructed to notify the investigator of any SAEs that occur within 30 days after administration of the last dose of study drug. Serious AEs will be followed until the SAE is stable or until resolution as determined by the investigator and/or medical monitor.

The total duration of the study for each subject, including the screening period, treatment period, the Day 36 (+2 days) end-of-study visit, and the Day 59 (+4 days) follow-up telephone call, will be approximately 87 days.

4. STUDY POPULATION

Approximately 44 healthy male and female subjects will be enrolled at a single center in the United States to achieve at least 36 evaluable subjects.

4.1 INCLUSION CRITERIA

Each subject must meet all of the following criteria to be enrolled in this study:

- 1. The subject is male or female 18 to 50 years of age, inclusive.
- 2. Blood phosphorus levels within normal laboratory reference range.
- 3. Women of childbearing potential have a negative β human chorionic gonadotropin pregnancy test (serum) at the screening visit and a confirmatory negative serum pregnancy test on Day –1 before receipt of study drug, and meet one of the following criteria:
 - a. The subject or their partner has undergone surgical sterilization
 - b. The subject is postmenopausal, defined as 12 consecutive months with no menses without an alternative medical cause and has a documented plasma follicle-stimulating hormone level >40 IU/mL
 - c. The subject agrees to be abstinent (ie, heterosexually inactive or women in a religious order)
 - d. The subject agrees to consistently use 1 of the following methods of contraception from the beginning of screening (which they had been consistently using for at least 30 days before the first dose of study drug) through 30 days after the last dose of study drug:
 - i. Condoms, male or female, with a spermicide

NOTE: For male subjects, condoms must be used for 90 days after last dose of study drug

- ii. Diaphragm or cervical cap with spermicide
- iii. Intrauterine device with spermicide
- iv. Oral contraceptives or other hormonal methods

NOTE: Another nonhormonal method of contraception must be used in conjunction with oral contraceptives

- v. Male sexual partner who had undergone a vasectomy at least 3 months before screening.
- 4. Male subjects must agree to not donate sperm from the first dose of study drug through 90 days after the last dose of study drug.
- 5. The subject is considered by the investigator to be in good general health as determined by medical history, clinical laboratory test results, vital sign measurements, 12-lead electrocardiogram (ECG) results, and physical examination findings at screening.
- 6. The subject agrees to comply with the dietary requirements.
- 7. The subject agrees to comply with all protocol requirements.
- 8. The subject is able to provide written informed consent.

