- 3. Women of childbearing potential have a negative β human chorionic gonadotropin pregnancy test (serum) at the screening visit and a confirmatory negative serum pregnancy test on Day –1 before receipt of study drug, and meet one of the following criteria:
 - a. The subject or their partner has undergone surgical sterilization
 - b. The subject is postmenopausal, defined as 12 consecutive months with no menses without an alternative medical cause and has a documented plasma follicle-stimulating hormone level >40 IU/mL

Protocol: SIGA-246-023 (Version 2.0)

- c. The subject agrees to be abstinent (ie, heterosexually inactive or women in a religious order)
- d. The subject agrees to consistently use 1 of the following methods of contraception from the beginning of screening (which they had been consistently using for at least 30 days before the first dose of study drug) through 30 days after the last dose of study drug:
 - i. Condoms, male or female, with a spermicide

NOTE: For male subjects, condoms must be used for 90 days after last dose of study drug

- ii. Diaphragm or cervical cap with spermicide
- iii. Intrauterine device with spermicide
- iv. Oral contraceptives or other hormonal methods

NOTE: Another nonhormonal method of contraception must be used in conjunction with oral contraceptives

- v. Male sexual partner who has undergone a vasectomy at least 3 months before screening.
- 4. Male subjects must agree to not donate sperm from the first dose of study drug through 90 days after the last dose of study drug.
- 5. Subject is considered by the investigator to be in good general health as determined by medical history, clinical laboratory test results, vital sign measurements, 12-lead electrocardiogram (ECG) results, and physical examination findings at screening.
- 6. Subject agrees to comply with the dietary requirements.
- 7. Subject agrees to comply with all protocol requirements.
- 8. Subject is able to provide written informed consent.

Exclusion Criteria:

Subjects meeting any of the following criteria will be excluded from the study:

- 1. Subject is a female who is pregnant or breastfeeding or planning to become pregnant within 3 months after the last dose of study drug.
- 2. Subject has a history of any clinically significant conditions including:
 - Asthma treated with oral systemic steroids within the past 6 months
 - Diabetes mellitus (type 1 or 2), with the exception of gestational diabetes

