 - White blood cell count considered to be clinically significant by the investigator
 - Absolute neutrophil count <1000 cells/mm³
 - Platelets not within $\pm 10\%$ of laboratory reference range
 - Alanine aminotransferase >2.0 times above the upper laboratory reference range

- Aspartate aminotransferase >2.0 times above the upper laboratory reference range
- Alkaline phosphatase >20% above the upper laboratory reference range
- Hemoglobin A1c \geq 7.0%
- Cholesterol ≥300 mg/dL and low-density lipoprotein ≥190 mg/dL.
- 29. Subject has a blood pressure considered to be clinically significant by the investigator. Blood pressure may be retested twice in the sitting position at 5-minute intervals.
- 30. Subject has a resting heart rate of <40 beats per minute or >110 beats per minute at screening.
- 31. Subject has an abnormal ECG at screening that is determined by the investigator to be clinically significant.
- 32. Male subject has a QT interval corrected using Fridericia's formula (QTcF) >450 ms or female subject has a QTcF >470 ms at screening or Day -1.
- 33. In the opinion of the investigator, the subject is not suitable for entry into the study.

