4.3 OTHER SCREENING CONSIDERATIONS

- Subjects must be willing to be confined to the study site until Day 31 (5 separate dosing periods).
- Subjects must be willing and agree to return for the end-of-study visit on Day 36 (+2 days) and answer a follow-up telephone call on Day 59 (+4 days).

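### Inclusion criterion 3a accepts a partner's sterilization with no minimum interval, so the 3-month vasectomy condition in 3d.v can never change an eligibility decision

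*Combined protocol and SAP*

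**What the plan says.** Criterion 3 in protocol Section 4.1 covers women of childbearing potential. They must have negative pregnancy tests "before receipt of study drug, and meet one of the following criteria". Four lettered items follow, and two of them deal with a sterilized partner.

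- Item 3a: "The subject or their partner has undergone surgical sterilization". It gives no interval.
- Item 3d.v, one of the contraceptive methods listed under 3d: "Male sexual partner who had undergone a vasectomy at least 3 months before screening".

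The synopsis repeats the pair. Its 3a has the same words, and its 3d.v reads "Male sexual partner who has undergone a vasectomy at least 3 months before screening". Neither the protocol nor the SAP defines surgical sterilization, and neither says that 3d.v takes precedence over 3a.

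The reason for the contraception rules is given in Section 1.4.1: "The effect of TPOXX on a fetus or nursing baby is not yet known". Women of childbearing potential are therefore "required to agree to use an acceptable means of birth control from signing of the informed consent form", continuing through 30 days after the last dose.

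**The concern.** Items 3a to 3d are alternatives, so meeting any one is enough. Item 3a takes in every partner vasectomy, however recent. Item 3d.v takes in only those at least 3 months old, which is a subset of what 3a already accepts. The 3-month condition is the protocol's own statement of when a partner's vasectomy can be relied on, and it has no effect as the criterion is built.

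A woman admitted through 3a also avoids the lead-in to 3d, which asks for at least 30 days of consistent use of the method before the first dose.

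What is at stake is fetal safety in a small group: a woman could take part while relying on a vasectomy that the protocol elsewhere treats as too recent. The pharmacokinetic comparison, the sample size and the error rates do not depend on this.

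**Working it through.** The plan gives no figure to reproduce here. The check has two parts: the logic of the criterion, and the length of time it could matter.

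**Logic.** Beyond the pregnancy tests, a woman is eligible under criterion 3 if 3a or 3b or 3c or any item of 3d holds. Take a partner vasectomy done *t* months before screening.

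- 3a is met for every *t*.
- 3d.v is met only if *t* ≥ 3.
- So 3d.v implies 3a, and adding 3d.v to the list admits nobody new.

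An enumeration confirms this. Cross 8 states of partner vasectomy (none, or 0.5, 1, 2, 2.9, 3, 6 or 24 months before screening) with yes or no for each of four other routes (subject sterilized, 3b, 3c, another 3d method): 8 × 2 × 2 × 2 × 2 = 128 profiles.

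| Change to criterion 3 | Decisions that change |
|---|---|
| Delete 3d.v | 0 of 128 |
| Keep 3d.v but drop its 3-month limit | 0 of 128 |
| Limit 3a to the subject, then drop the 3-month limit | 4 of 128 |

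The 4 profiles are vasectomies at 0.5, 1, 2 and 2.9 months with no other qualifying route. These are the cases that the limit was written for.

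**Does other text restore the limit?** Section 1.4.1 sets no interval for vasectomy. Exclusion 33 is a matter of judgement: "In the opinion of the investigator, the subject is not suitable for entry into the study". The change history does not list criterion 3.

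**Length of time at issue.** Inputs for a subject who completes all periods:

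- Screening on Day -28 to Day -2 (Section 3).
- Last dose on Day 29 and discharge on Day 31 (Table 9-2). Section 4.3 has the matching condition: "Subjects must be willing to be confined to the study site until Day 31".
- Contraception through 30 days after the last dose (3d): 29 + 30 = Day 59, which agrees with Table 9-2, note (c).
- No Day 0 (the study-day rule in SAP Section 4).
- Assumption: 3 months = 90 days.

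Time outside confinement while contraception is still required: 59 − 31 = 28 days.

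Days from screening to discharge:
- Screening on Day -28: 28 + 30 = 58.
- Screening on Day -2: 2 + 30 = 32.

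A vasectomy done just before screening is therefore 32 to 58 days old at discharge. Adding 28, it is 60 to 86 days old on Day 59, and so under 90 days throughout.

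In general, let *v* be the days from vasectomy to screening and *a* the days from screening to discharge. The days after discharge with the vasectomy under 90 days old are max(0, min(28, 90 − *v* − *a*)).

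| | Screening Day -28 (*a* = 58) | Screening Day -2 (*a* = 32) |
|---|---|---|
| All 28 days affected | *v* ≤ 4 | *v* ≤ 30 |
| *v* = 30 | 90 − 30 − 58 = 2 days | 90 − 30 − 32 = 28 days |
| No days affected | *v* ≥ 32 | *v* ≥ 58 |

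The 1 to 27 days from screening to Day -1 are left out, because no drug has been given and a pregnancy test follows on Day -1.

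**The case against.** The strongest reply is that surgical sterilization is undefined. Vasectomy is named only in 3d.v, so a site could apply that specific item to vasectomy and read 3a as meaning established sterility. Criterion 3 is loosely drafted in other respects: a list for women of childbearing potential includes postmenopausal women and a condom note for male subjects. Section 1.4.1 could also be read as pointing back to the protocol's own list when it asks for acceptable contraception. The enumeration takes the ordinary meaning of sterilization as given, so it cannot settle that question.

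Sites may well act this way, but nothing in the text tells them to. Vasectomy is the ordinary form of surgical sterilization in a man, and without it the mention of the partner in 3a would have almost no content. A woman enrolled through 3a with a recently vasectomized partner would not be a protocol deviation.

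The reply is stronger on size:

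- Section 6.2.1.8 requires counselling on avoiding pregnancy, which also bears on the period after discharge.
- The design treats 7 days as enough washout between doses. On that yardstick the Day 29 dose is cleared by Day 36, only 5 days after discharge. This is an inference, since the documents give no half-life, and the protocol still asks for 30 days of contraception.
- The group affected needs a very recent partner vasectomy and no other qualifying method.
- The SAP title page is dated 28 June 2023 and its schedule notes are in the past tense, so conduct may be over.

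These points support a minor rating. They do not make the 3-month condition work.

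**Conclusion.** The criterion is wrong as written, and the consequence is minor. Taking vasectomy as surgical sterilization, the 3-month condition cannot exclude anyone. The exposure is at most 28 days after discharge for a completer. It falls to zero once the vasectomy was done 32 days (screening on Day -28) to 58 days (screening on Day -2) before screening, with 3 months taken as 90 days. The documents do not say how many subjects rely on partner sterilization, so no count can be given.

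Exclusion of pregnant women, stopping of dosing on pregnancy, confinement, counselling and the investigator's discretion all remain as protection. Pregnancy testing helps less in the window at issue: the schedule of events shows no test after check-in on Day -1, and although Section 1.4.1 refers to Day -1 of each period, that is still before discharge.

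**What to change.** In Section 4.1 and the synopsis, limit 3a to surgical sterilization of the subject herself and leave partner vasectomy to 3d.v. The alternative is to keep the partner in 3a and attach the same minimum of 3 months before screening to that clause.

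Either way it is one wording edit made in two places, with no change to procedures, sample size or analysis. If enrolment has ended, all that remains is to correct the wording before the criterion is reused in another protocol.

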4.2 EXCLUSION CRITERIA

Subjects meeting any of the following criteria will be excluded from the study:

- 1. Subject is a female who is pregnant or breastfeeding or planning to become pregnant within 3 months after the last dose of study drug.
- 2. Subject has a history of any clinically significant conditions including:
 - Asthma treated with oral systemic steroids within the past 6 months
 - Diabetes mellitus (type 1 or 2), with the exception of gestational diabetes
 - Hypertension that is poorly controlled (repeat readings >140 mm Hg systolic and/or >90 mm Hg diastolic)
 - Thyroidectomy or thyroid disease that required medication within the past 12 months
 - Serious angioedema episodes within the previous 3 years or requiring medication in the previous 2 years
 - Head trauma resulting in a diagnosis of traumatic brain injury other than concussion
 - Frequent episodes of headache.

- 3. Subject has received treatment in another clinical study of an investigational drug (or medical device) within 30 days or 5 half-lives (whichever is longer) before the first dose of study drug.
- 4. Subject has a history of relevant drug and/or food allergies (ie, allergy to TPOXX or excipients, or any significant food allergy that could preclude a standard diet in the study site).
- 5. Subject has any condition possibly affecting drug absorption (eg, previous surgery on the gastrointestinal tract, including removal of parts of the stomach, bowel, liver, gallbladder, or pancreas, with the exception of appendectomy).
- 6. Subject has evidence or history of clinically significant allergic (except for untreated, asymptomatic, seasonal allergies at time of the first dose of study drug), hematological, endocrine, pulmonary, gastrointestinal, cardiovascular, hepatic, psychiatric, or neurological disease. Exceptions to these criteria (eg, stable, mild joint disease unassociated with collagen vascular disease) may be made following discussions with the medical monitor.
- 7. Subject has a history of cardiac disease, symptomatic or asymptomatic arrhythmias, syncopal episodes, or risk factors for torsades de pointes (eg, heart failure, hypokalemia).
- 8. Subject has a family history of sudden cardiac death not clearly due to acute myocardial infarction.
- 9. Subject has a seizure disorder or history of seizures (does not include childhood febrile seizures) or a past history that increases seizure risks such as significant head injury that caused loss of consciousness or other changes in the subject's daily function, concussion, stroke, central nervous system infection or disease, or alcohol or drug abuse or family history of idiopathic seizures.
- 10. Subject has a history of a peptic ulcer or significant gastrointestinal bleeding.
- 11. Subject has a bleeding disorder diagnosed by a doctor (eg, factor deficiency, coagulopathy, or platelet disorder requiring special precautions) or significant bruising or bleeding difficulties with blood draws.
- 12. Subject has a malignancy that is active, or treated malignancy for which there is not reasonable assurance of sustained cure, or malignancy that is likely to recur during the period of the study (subject should be in complete remission for at least 5 years).

- 13. Subject has neutropenia or other blood dyscrasia determined to be clinically significant by the investigator.
- 14. Subject has used any of the following prohibited medications from within 7 days (or 5 half-lives, whichever is longer) before the first dose of study drug: antidiabetic medication; anticoagulants; anticonvulsants; substrates of the breast cancer resistance protein transporter including methotrexate, mitoxantrone, imatinib, irinotecan, lapatinib, rosuvastatin, sulfasalazine, and topotecan; substrates of CYP2C8 including repaglinide, paclitaxel, Montelukast, pioglitazone, rosiglitazone; and substrates of CYP2C19 including S-mephenytoin, clobazam, diazepam, rabeprazole, voriconazole, lansoprazole, and omeprazole. Medications not listed here that are known (or thought) to be CYP3A4 substrates may be allowed at the investigator's discretion, after consultation with the medical monitor, if administration poses little to no risk to the subject.
- 15. Subject has a history of drug or alcohol abuse or dependency within the last year before screening.
- 16. Subject has a current or recent (<30 days before screening) history of clinically significant bacterial, fungal, or mycobacterial infection.
- 17. Subject has a current clinically significant viral infection.
- 18. Subject has a known clinically significant chronic viral infection (eg, human T cell lymphotropic virus I or II).
- 19. Subject has consumed grapefruit or grapefruit juice, Seville orange or Seville orange-containing products (eg, marmalade), or caffeine- or xanthine-containing products within 48 hours before the first dose of study drug.
- 20. Subject has used any prescription (excluding hormonal birth control) or over-the-counter medication (including herbal or nutritional supplements) within 14 days before the first dose of study drug.
- 21. Subject demonstrates long-term use (≥14 consecutive days) of glucocorticoids including oral or parenteral prednisone or equivalent (>20 mg total dose per day) or high-dose inhaled steroids (>800 mcg/day of beclomethasone dipropionate or equivalent) within the preceding 1 month (low-dose [≤800 mcg/day of beclomethasone dipropionate or equivalent] inhaled and topical steroids are allowed).

- 22. Subject has donated >450 mL blood or blood components within 30 days before the first dose of study drug. The investigator should instruct subjects who participate in this study to not donate blood or blood components for 4 weeks after the completion of the study.
- 23. Subject is a smoker or has used nicotine or nicotine-containing products (eg, cigarettes, electronic vapor cigarettes, cigars, chewing tobacco, snuff, nicotine patches, or nicotine gum) within 6 months before the first dose of study drug.
- 24. Subject has consumed pomegranate or pomegranate juice, pomelo fruits or pomelo juice, or alcohol within 72 hours before the first dose of study drug.
- 25. Subject reports participation in strenuous activity or contact sports within 24 hours before the first dose of study drug.
- 26. Subject has known hepatitis B or C infection or positive test for hepatitis B surface antigen, hepatitis C virus antibody, or human immunodeficiency virus type 1 or 2 antibodies at screening.
- 27. Subject has a positive test result for amphetamines (including methamphetamines and ecstasy/methylenedioxymethamphetamine), barbiturates, benzodiazepines, cannabinoids (including tetrahydrocannabinol), cocaine metabolites, opiates (including heroin, codeine, and oxycodone), or alcohol at screening or check-in.
- 28. Subject has any of the following laboratory test results within 28 days before the first dose of study drug:
 - Estimated serum creatinine clearance (Cockcroft-Gault) <70 mL/min
 - Creatinine in males >1.7 mg/dL and in females >1.4 mg/dL (1.3 times the upper laboratory reference range)
 - Hemoglobin ≤10% of the lower laboratory reference range
 - White blood cell count considered to be clinically significant by the investigator
 - Absolute neutrophil count <1000 cells/mm³
 - Platelets not within $\pm 10\%$ of laboratory reference range
 - Alanine aminotransferase >2.0 times above the upper laboratory reference range

- Aspartate aminotransferase >2.0 times above the upper laboratory reference range
- Alkaline phosphatase >20% above the upper laboratory reference range
- Hemoglobin A1c \geq 7.0%
- Cholesterol ≥300 mg/dL and low-density lipoprotein ≥190 mg/dL.
- 29. Subject has a blood pressure considered to be clinically significant by the investigator. Blood pressure may be retested twice in the sitting position at 5-minute intervals.
- 30. Subject has a resting heart rate of <40 beats per minute or >110 beats per minute at screening.
- 31. Subject has an abnormal ECG at screening that is determined by the investigator to be clinically significant.
- 32. Male subject has a QT interval corrected using Fridericia's formula (QTcF) >450 ms or female subject has a QTcF >470 ms at screening or Day -1.
- 33. In the opinion of the investigator, the subject is not suitable for entry into the study.

